**Statistical Analysis Plan:**

This is an open-label study. The number of subjects was chosen based on feasibility and is considered sufficient to meet the study objectives. Detailed methodology for summary and statistical analyses of the data collected in this study will be documented in the Clinical Study Report. Mean and standard deviation will be used for continuous data.

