## BACKGROUND

The AEON™ Endostapler is comprised of a stapler handle and reloads. The handle may accept multiple reloads of single fire cartridges. The AEON™ Endostapler devices are CE certified per Certificate No. G1 003029 0001 Rev. 00. The AEON™ Endostapler devices were cleared by the United States Food and Drug Administration (FDA) under the 510(k) process. Pertinent applications numbers are K171589 and K173443.

The AEON™ Endostapler has previously been proven as safe and effective for bariatric surgery as presented by Cleveland Clinic at SAGES 2019. The AEON™ Endostapler also has been evaluated for superior hemostasis against the Ethicon stapler with research led by [name], as referenced inclinicaltrials.gov:

<https://clinicaltrials.gov/ct2/show/NCT04149925?term=AEON+or+%27Lexington+medical%27&draw=2&rank=1>.

This study aims to demonstrate safety and effectiveness for thoracic surgery.

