### **Primary Outcome Measure:**

- Incidence of reported device-related adverse events through 30-day post-operative evaluation period

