### **Secondary Outcome Measures:**

- Incidence of product malfunction during procedure

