## **METHODS**

The study will include 80 total procedures on consecutive patients which will be performed by either [name] or [name] using the AEON™ Endostapler.

All patients will undergo the standard preoperative evaluation pathway.

On the day of surgery, the surgeon will elect to use the AEON™ Endoscopic Stapler Reloads. The surgeon should read and follow the Instructions for Use and use their own clinical judgement when determining the appropriate products to use. If the reloads are used, and it is clinically appropriate, reloads from other manufacturers should not be used for that case. However, in the event of unavailability of a clinically appropriate AEON™ Endoscopic Stapler Reload, a similar reload from another manufacturer is

allowed. At the end of each case, a member of the surgical or nursing team will fill out the Case Report Form.

All typical post-operative care will continue, including during the immediate post-operative period prior to hospital discharge. Regularly scheduled follow up appointments will be scheduled based on the preference and practice pattern of the surgeon and institution.

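### The plan gives no analysis or interval for its two Yes/No outcomes and sets a demonstration aim that one arm without a threshold cannot meet; the design supports estimation only

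*Combined protocol and SAP*

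**What the plan says.** The primary outcome is "Incidence of reported device-related adverse events through 30-day post-operative evaluation period" and the secondary outcome is "Incidence of product malfunction during procedure". Appendix A (Case Report Form) records each as a single Yes or No per case.

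The Statistical Analysis Plan section is four sentences long. Besides noting the open-label design, it says:

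- on sample size: "The number of subjects was chosen based on feasibility and is considered sufficient to meet the study objectives";
- on methods: "Detailed methodology for summary and statistical analyses of the data collected in this study will be documented in the Clinical Study Report";
- on summaries: "Mean and standard deviation will be used for continuous data".

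The purpose is worded in two ways. The Objectives section speaks of evaluating the device. The Background ends with "This study aims to demonstrate safety and effectiveness for thoracic surgery". No comparator, performance goal, expected rate or confidence interval is given.

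The size is also stated in two ways. One sentence in Objectives gives 30 patients. The enrollment line in the same section gives 80, and Methods agrees: "The study will include 80 total procedures on consecutive patients". That conflict is a separate matter and enters here only because it changes the precision.

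On follow-up, Methods says: "Regularly scheduled follow up appointments will be scheduled based on the preference and practice pattern of the surgeon and institution". The form is to be completed when the case ends, yet it carries a 30-day item, and that item can be answered only Yes or No. Methods also allows another manufacturer's reload when no suitable AEON reload is available. The malfunction item on the form does not say whose product it means.

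**The concern.** The one method that the plan names applies to neither outcome. On the form it fits only age and the reload counts. How the two incidences are summarised, and with what uncertainty, is left to a document written after the open-label data are in.

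This matters because of the claim attached to the result. If no events are reported, the plan as written allows a bare 0/80 to be set beside the Background's aim and read as safety shown. A reader would not be told which true rates remain compatible with that result.

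For the primary outcome the denominator is open as well. A patient not seen or contacted at day 30 has no category on the form. Whether that patient becomes a No, is left out, or is counted in some other way would be decided after the results are known.

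**Working it through.** **Inputs from the document.** N is 80 (Objectives enrollment line; Methods) or 30 (Objectives text). Both outcomes are Yes/No per case (Appendix A). No alpha, power, expected rate, margin or precision target is stated, so there is no sample-size calculation to reproduce.

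**Assumptions made here.** Two-sided 95% confidence, small event counts, illustrative numbers of patients with unknown 30-day status, and illustrative performance goals. None of these comes from the document.

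**Formula.** Exact (Clopper-Pearson) limits for x events in n patients: lower = Beta quantile(0.025; x, n − x + 1); upper = Beta quantile(0.975; x + 1, n − x). For x = 0 the lower limit is 0 and the upper limit reduces to 1 − 0.025^(1/n).

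**Step 1: precision with complete follow-up.** For zero events, 1 − 0.025^(1/80) = 0.0451 and 1 − 0.025^(1/30) = 0.1157.

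| Events | N = 80: 95% CI | N = 30: 95% CI |
|---|---|---|
| 0 | 0% to 4.5% | 0% to 11.6% |
| 1 | 0.03% to 6.8% | 0.08% to 17.2% |
| 2 | 0.3% to 8.7% | 0.8% to 22.1% |

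Seeing no event is also weak evidence in itself: at an assumed true rate of 1%, the chance of no event in 80 patients is 0.99^80 = 0.448.

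**Step 2: can sufficiency be judged?** Only against a target, and the answer depends on which one. Take one-sided alpha 0.025 and N = 80.

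- Assumed goal of 5%: met only with 0 events (0.95^80 = 0.0165). Power at a true 1% is 44.8%.
- Assumed goal of 10%: met with up to 2 events (exact alpha 0.0107). Power at a true 1% is 95.3%.

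With N = 30 neither goal can be met even with no events, since 0.95^30 = 0.215 and 0.90^30 = 0.042 both exceed 0.025.

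**Step 3: unknown 30-day status, with no reported events.** Counting unknowns as No always gives 0/N: an upper limit of 4.5% at 80 or 11.6% at 30.

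| Unknown | Known status only: upper limit | Unknowns counted as events (extreme bound) |
|---|---|---|
| 4 of 80 | 0/76: 4.7% | 4/80 = 5.0% (1.4% to 12.3%) |
| 8 of 80 | 0/72: 5.0% | 8/80 = 10.0% (4.4% to 18.8%) |
| 16 of 80 | 0/64: 5.6% | 16/80 = 20.0% (11.9% to 30.4%) |
| 3 of 30 | 0/27: 12.8% | 3/30 = 10.0% (2.1% to 26.5%) |

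Leaving unknowns out moves the upper limit little. The wide spread comes from the extreme bound.

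**The case against.** The other side has good points, and several of them stand.

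- **Feasibility sizing is normal in a descriptive post-market study.** The sufficiency sentence refers to the study objectives, and the section of that name only speaks of evaluating. A reader might infer that 80 is too few, or that the plan flatly contradicts itself. Neither is supported: against the Objectives section, sufficiency is unquantified rather than false. The conflict is with the closing sentence of the Background.
- **An incidence of a once-per-case Yes/No item already implies n/N.** This is fair, especially for malfunction, and anyone can compute an interval from 0/80. Not naming n/N would alone be missing detail. It matters here because it comes with a demonstration aim and an unquantified claim of sufficiency.
- **Documenting methods in the report does not prove that they are chosen after seeing the data.** That is correct. The text permits this but does not say that it will happen.
- **Downward bias is not certain.** A reader might infer that the primary incidence is necessarily biased. It is understated only if unknown patients are counted as No and some of them had an event. The outcome is worded as reported events, so a No where nothing was reported can be defended literally. The document gives no rate of loss to follow-up.
- **The text available is incomplete.** Material between Methods and the Statistical Analysis Plan was not available for this review. The statement that no rule covers unknown 30-day status holds for the visible text only.

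**Conclusion.** The point holds as one about analysis and claim, and it should be corrected. The Statistical Analysis Plan states no method or interval for either outcome. One arm without a threshold supports estimation and cannot by itself carry the Background's aim. If no events are reported, true rates up to 4.5% (N = 80) or 11.6% (N = 30) are not excluded at two-sided 95% confidence with complete follow-up.

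The follow-up part is conditional: it rests on the visible text, on some patients having unknown status at day 30, and on at least one of them having had an event. The gap does not invalidate the data collected, and it does not show that the planned number is wrong.

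**What to change.** 1. **Background and Objectives.** Replace the aim in "This study aims to demonstrate safety and effectiveness for thoracic surgery" with: to estimate the incidence of device-related adverse events and of product malfunction. Keep the verb evaluate in Objectives, but align its reference to safety and efficacy with these two incidences.
2. **Sample-size statement.** Once 30 and 80 are reconciled, replace the sufficiency claim with the precision delivered under complete follow-up. At 80, 0, 1 or 2 events give upper exact 95% limits of 4.5%, 6.8% or 8.7%. At 30, they give 11.6%, 17.2% or 22.1%.
3. **Analysis text, replacing the deferral.** Report each incidence per patient as n/N with an exact two-sided 95% confidence interval.
   - Malfunction: N is all patients in whom the AEON device was used; a case is a patient with at least one malfunction of an AEON product.
   - 30-day device-related adverse events: N is treated patients who either had an event reported at any time up to day 30 or are known to be event-free at day 30. This keeps a patient with an early event who is later lost.
   - Report the number with unknown status, and add a sensitivity analysis counting them as events, labelled an extreme bound.
4. **Case Report Form.** Add an Unknown option to the 30-day item, and specify that the malfunction item refers to AEON products.

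The cost is a short paragraph, a reworded aim and two small form edits. It needs no extra patients, and the analysis work is trivial. If forms have already been completed, each No at 30 days should be checked against known status. The downsides are a narrower stated aim, a less favourable precision statement, and a worst-case figure that may look high if many patients are unknown.

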**Appendix A – Case Report Form**

Surgery Date: \_\_\_\_\_ Surgeon: \_\_\_\_\_ Hospital: \_\_\_\_\_

Surgery Type: \_\_\_\_\_

Patient Gender: \_\_\_\_\_ Patient Age: \_\_\_\_\_

AEON Endostapler	Black 60mm	Purple 60mm	Purple 45mm	Orange 60mm	Orange 45mm	White 60mm	White 45mm	Gray 45mm
Quantity Non-Curved Tip Reloads Used								
Quantity Curved Tip Reloads Used								

Intraoperative Outcomes								
Product malfunction during stapling? (circle one)					Yes	No		
Blood transfusion due to staple line bleeding? (circle one)					Yes	No		

*If yes to any above, please specify:*

30 Day Postoperative Outcomes		
Reported device-related adverse events? (circle one)	Yes	No

*If yes to any above, please specify:*

Investigator Signature: \_\_\_\_\_

Date: \_\_\_\_\_

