## **OBJECTIVES**

The goal of this post-market study is to evaluate safety and efficacy of the AEON™ Endostapler when used in VATS or open lung resection surgery (lobectomy or wedge resection). Patients eligible will be over the age of 18 and undergoing planned lobectomy or wedge resection. The study will include 30 total consecutive patients that meet eligibility criteria. The procedures will be performed according to institutional standard-of-care and all subjects will undergo standard preoperative evaluation as well as postoperative care. Relevant data will be collected using the Case Report Form which should be filled out following each procedure by a member of the surgical or nursing team.

**Enrollment:** 80 Subjects Meeting Inclusion/Exclusion Criteria

**Investigator Masking:** None (Open Label)

**Device:** AEON™ Endostapler

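### Effectiveness in lung resection is claimed, but air leak is neither asked on the Case Report Form nor listed as an outcome, so the leak rate cannot be estimated

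*Combined protocol and SAP*

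**What the plan says.** The Objectives section states that the study will "evaluate safety and efficacy of the AEON™ Endostapler when used in VATS or open lung resection surgery (lobectomy or wedge resection"). The Background section adds: "This study aims to demonstrate safety and effectiveness for thoracic surgery".

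Two outcomes are declared. The primary is "Incidence of reported device-related adverse events through 30-day post-operative evaluation period" and the secondary is "Incidence of product malfunction during procedure". Neither section defines its event or says who decides that an event is due to the device.

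Appendix A has three outcome items, each answered Yes or No:

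- "Product malfunction during stapling" (intraoperative)
- "Blood transfusion due to staple line bleeding" (intraoperative)
- "Reported device-related adverse events" (30 days)

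Free text is requested only after a positive answer: "If yes to any above, please specify". Air leak, leak testing and chest drain duration appear in neither the outcome measures nor the form.

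**The concern.** In lobectomy and wedge resection the staple line has to hold air as well as blood. Three features of the plan make the missing item matter here.

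- According to Background, the device has already been evaluated in bariatric surgery and for hemostasis. Thoracic use is the new question, yet the one item that names the staple line is again about bleeding.
- The exclusion criteria rule out reinforcement material, so the study observes the unreinforced staple line but does not ask whether it sealed.
- There is no comparator, so any statement about effectiveness has to come from what is recorded for every patient.

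If the plan is followed exactly, the report can give malfunction and device-related event counts but no systematic evidence on whether the lung was sealed. A leak dealt with during surgery and not written down then may not be recoverable afterwards.

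**Working it through.** **Step 1. Can each form item capture an air leak?**

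| Form item | Names the staple line? | Would it record an air leak? |
|---|---|---|
| Product malfunction | No | Only if the team regards the leak as a malfunction; term undefined |
| Transfusion for staple-line bleeding | Yes | No; concerns bleeding |
| Device-related adverse event, 30 days | No | Only if reported and judged device-related; no rule given |

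A leak therefore reaches the data through a judgement in two of the three items and is never asked about directly.

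**Step 2. What that judgement does to the count.** The documents state no leak rate and no power calculation, so there is no figure of the plan's own to reproduce. Let n be the number of patients, L the proportion with a leak, and q the chance that a leak is entered as a malfunction or device-related event. L and q are assumptions.

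- Expected leaks = n × L. Expected recorded leaks = n × L × q.
- Chance that leaks produce no Yes at all = (1 − L × q)^n.

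Example: with n = 80, L = 10% and q = 25%, 80 × 0.10 = 8 leaks are expected, of which 8 × 0.25 = 2 are recorded. The form estimates the product L × q. As q is unknown, L cannot be recovered from it.

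Chance of no Yes arising from leaks:

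| n | L | q = 5% | q = 10% | q = 25% | q = 50% |
|---|---|---|---|---|---|
| 80 | 10% | 0.67 | 0.45 | 0.13 | 0.02 |
| 80 | 30% | 0.30 | 0.09 | 0.002 | <0.001 |
| 30 | 30% | 0.64 | 0.40 | 0.10 | 0.008 |

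Complete silence is plausible when attribution is rare and unlikely when leaks are frequent and attribution is not rare. Under-counting occurs whenever q is below 1.

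**Step 3. What a zero would mean.** For 0 of n, the one-sided 95% upper limit is 1 − 0.05^(1/n): 3.7% for n = 80 and 9.5% for n = 30. That limit applies to reported device-related events, not to air leak.

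**Step 4. What asking directly would give.** Assume a prolonged-leak rate of 5-15% (not from the documents). Enrolment is given as 80 in Methods and in the enrolment line of Objectives, but as 30 in the Objectives text.

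- n = 80: 80 × 0.05 = 4 to 80 × 0.15 = 12 cases. The exact (Clopper-Pearson) 95% interval is 1.4-12.3% for 4/80 and 8.0-24.7% for 12/80.
- n = 30: 30 × 0.05 = 1.5 to 30 × 0.15 = 4.5 cases. At 5%, the chance of seeing none is 0.95^30 = 0.21, against 0.95^80 = 0.02 with 80 patients.

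**The case against.** The strongest reply is that leaks can be recorded under the present form. Malfunction is undefined, so a surgeon could enter a leaking fresh staple line there and describe it. The primary outcome runs through 30 days and does not clearly exclude events during surgery. This stands: leaks are unsolicited, not uncapturable.

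A reader might go further and infer that a repaired leak leaves no trace, or that a stapler leaking in many patients would be expected to return No throughout. The documents do not support either inference. They do not say that a leak is not a malfunction, and at a 30% leak rate with 25% attribution in 80 patients the chance of an all-No result from leaks is only 0.002. But what would then be recorded is still a count filtered by attribution, not a leak rate.

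Three further points stand. The malfunction item is itself a measure of device performance. The form does serve both declared outcomes. And new leak data would not tell a good stapler from a poor one: there is no comparator or performance threshold, other manufacturers' reloads are allowed when a suitable one is unavailable, and some leaks reflect lung disease. That limits what the added data can prove, but it does not justify leaving them out.

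**Conclusion.** The concern holds in this form: effectiveness in lung resection is claimed, air leak is not solicited, and a leak is recorded only through two undefined judgements. Under-counting is likely, and the leak rate cannot be estimated from the planned data. The declared outcomes can still be reported, so this is a change that should be made, not a fatal flaw.

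The absence of an air-leak item is a matter of text and needs no assumption. The size does: the leak rates and attribution chances above are illustrative, and precision depends on whether 30 or 80 patients are enrolled. One section between Methods and the Statistical Analysis Plan was not available for this check. A definition there could narrow the ambiguity, but the form itself has no air-leak item.

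**What to change.** Add to Appendix A, for every patient whatever the presumed cause:

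1. Staple-line air leak or bleeding seen during the operation that needed an additional intervention (Yes/No, specify).
2. Prolonged air leak, under one definition that the investigators fix before data collection and print on the form (Yes/No), with the date of last chest drain removal.

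Record device-relatedness as a separate answer, so that attribution does not decide whether the leak is counted. Under Secondary Outcome Measures, list staple-line air leak (intraoperative; prolonged), reported as number, percent and exact 95% interval. Reconcile the 30 and 80 patient statements so that the expected precision can be stated.

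The cost is a few form lines and one more secondary outcome, based on what the team sees at operation and during usual post-operative care. Patient care does not change. The downsides are a possibly less favourable number in the report, some leaks that reflect lung disease, and a result that remains descriptive.

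### After closure, staple line bleeding has no item of its own on the form and reaches the 30-day primary outcome only if reported as device-related, so it is likely to be under-counted.

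*Combined protocol and SAP*

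**What the plan says.** The primary outcome is "Incidence of reported device-related adverse events through 30-day post-operative evaluation period". The only secondary outcome is "Incidence of product malfunction during procedure". Neither bleeding nor transfusion is a listed outcome, and the Statistical Analysis Plan describes no analysis of either.

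The Case Report Form in Appendix A has two outcome blocks:

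- **"Intraoperative Outcomes"** holds two Yes/No items: product malfunction, and "Blood transfusion due to staple line bleeding? (circle one".
- **"30 Day Postoperative Outcomes"** holds one Yes/No item: "Reported device-related adverse events? (circle one".

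Each block is followed by a free-text line for details of any Yes answer, and the form ends with an investigator signature.

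On timing, Methods says "At the end of each case, a member of the surgical or nursing team will fill out the Case Report Form". On follow-up it says "Regularly scheduled follow up appointments will be scheduled based on the preference and practice pattern of the surgeon and institution". The study is open label (Objectives).

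**The concern.** The form treats one complication in two ways, depending on when it is treated. If blood is given for a bleeding staple line during surgery, the form asks about it by name. If blood is given in the recovery room or on the ward, or the patient returns to theatre, no item names the event. It enters the data only after two further steps: someone must report it, and someone must attribute it to the device. The text available for review does not define device-related or say who decides.

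The second route is the weaker one here. The study is unblinded, follow-up visits follow local habit, and the cause of a bleed after lung resection is often open to judgement. Missed or unattributed events can only lower the count, so the error runs in the device's favour. At stake is the completeness of the one safety outcome that the study exists to report. A lesser risk is that the intraoperative figure is later read as the bleeding rate for the whole period.

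**Working it through.** **No figure to reproduce.** The documents give no bleeding rate, event rate, power or threshold, and the sample size rests on feasibility. The main check is to set the items side by side.

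| Event | Named item on the form? | What must happen for it to be recorded |
|---|---|---|
| Transfusion for staple line bleeding, during surgery | Yes, intraoperative block | A Yes on that item |
| Transfusion for staple line bleeding, after surgery | No | Reported and judged device-related, then a Yes on the generic 30-day item |
| Return to theatre for staple line bleeding | No | As above |

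The last two rows fall inside the 30-day window of the primary outcome.

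**Illustration for the existing item.** Inputs:

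- N = 80, from Methods and the enrollment line in Objectives. (Objectives also states 30 patients, a separate inconsistency.)
- p = true rate of transfusion for staple line bleeding through day 30. Assumed: 3% or 5%.
- f = share of those transfusions given after closure. Assumed: 0, 25%, 50% or 75%.

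Expected cases on the item = N·p·(1−f). Chance that it shows none = (1 − p(1−f))^N.

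| p | f | Expected on item | Chance of 0 of 80 |
|---|---|---|---|
| 5% | 0 | 80 × 0.05 = 4 | 0.95^80 = 1.7% |
| 5% | 25% | 3 | 0.9625^80 = 4.7% |
| 5% | 50% | 2 | 0.975^80 = 13% |
| 5% | 75% | 1 | 0.9875^80 = 37% |
| 3% | 0 | 80 × 0.03 = 2.4 | 0.97^80 = 8.7% |
| 3% | 25% | 1.8 | 0.9775^80 = 16% |
| 3% | 50% | 1.2 | 0.985^80 = 30% |
| 3% | 75% | 0.6 | 0.9925^80 = 55% |

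A lower rate gives the same pattern. At p = 2%, the chance of at least one case is 80% over the whole period. On the intraoperative item alone it is 70%, 55% or 33% for f = 25%, 50% or 75%. In every row the item recovers the fraction (1−f) of the full-period count.

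**What this implies for the primary outcome.** Let r be the chance that a post-closure case is reported and judged device-related. If every such case is truly device-related, the expected shortfall is N·p·f·(1−r). It is zero at r = 1 and at most N·p·f at r = 0. With p = 5% that maximum is 4 × 0.25 = 1, 4 × 0.50 = 2 or 4 × 0.75 = 3 cases in 80. With p = 3% it is 0.6, 1.2 or 1.8. The documents give no value for p, f or r, so only the sign of the shortfall is established.

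**The case against.** The other side has a strong case, and much of it stands.

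- **The event is within a question on the form.** A reader might infer that bleeding after closure is never asked about. That is not so. The generic 30-day item covers a later staple line bleed judged device-related, requires a Yes or No, and has space for details. What is missing is a specific prompt that does not depend on attribution.
- **There is no bleeding result to distort.** A reader might infer that the study's bleeding rate will read low. The plan lists no bleeding outcome and no bleeding analysis, and the item is accurate for the period its heading names. It misleads only if presented as covering more. The plan does not propose that, but it leaves detailed methods to the Clinical Study Report and so does not rule it out.
- **The probabilities concern an item that is not an outcome.** This is correct. No decision rule turns on seeing 0 of 80, and the loss in the primary outcome is only bounded.
- **Unprompted capture affects every complication.** This is true. Bleeding differs only in that the sponsor already chose to ask about it by name and stopped at the end of surgery.
- **Hemostasis is not an objective of this study.** Background mentions it in connection with a separate comparison, so the point should not lean on it.
- **Form timing is a separate defect.** Completing the form at the end of the case conflicts with its 30-day block wherever the transfusion row sits.

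Part of the document between Methods and the Statistical Analysis Plan was not available, so event-reporting text there cannot be assumed absent. The layout of the form is fully visible.

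None of this removes the uneven ascertainment of the same event before and after closure.

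**Conclusion.** The point holds as a gap in ascertainment. Staple line bleeding treated after closure has no specific item and depends on reporting and attribution in an open-label study, so it is likely to be under-counted in the 30-day primary outcome. The direction, towards a more favourable result for the device, follows from the structure of the form. The size does not: it depends on the bleeding rate, the share after closure and the reporting probability, none of which the documents give. It would be zero if every late bleed were reported and attributed. A reader might take the tabulated probabilities as a measured bias in the primary outcome; they are not, because they describe the intraoperative item under assumed rates. A transfusion rate from that item covers the operation only and must not be presented as a perioperative or 30-day rate. This is an inexpensive improvement worth making. It does not invalidate the plan.

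**What to change.** In the 30-day block of the Case Report Form, add two rows:

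- *Blood transfusion after leaving the operating room? Yes / No*
- *Return to operating room for bleeding? Yes / No*

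For each Yes, record the source as staple line, other or unknown. Complete both rows from the hospital chart at day 30.

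In the Statistical Analysis Plan, state that staple line bleeding requiring transfusion or re-exploration will be reported descriptively from incision through day 30, with the intraoperative part shown separately. Count cases with a staple line source in the primary outcome. Show unknown-source cases only in a sensitivity analysis, since counting them in the main result would turn a device-related outcome into a partly all-cause one.

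The cost is two extra form rows, a chart check at day 30 and a short addition to the Statistical Analysis Plan, with no added visit or procedure. The reported event rates may be slightly less favourable.
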